4.2.1 Registration Process for DF/HCC Sites

DF/HCC Standard Operating Procedure for Human Subject Research Titled *Subject Protocol Registration* (SOP #: REGIST-101) must be followed.

Following registration, patients will be randomized to the metformin/placebo. Initiation of metformin/placebo should begin within 4 weeks of screening/baseline blood collection.

5. TREATMENT PLAN

We will conduct a randomized placebo-controlled trial in patients with higher-risk monoclonal gammopathy of undetermined significance (MGUS) and low-risk smoldering multiple myeloma (SMM). After informed consent is signed, total of 60 eligible and evaluable participants will be randomized 1:1 either to metformin or placebo. Stratification factors will be disease stage (MGUS vs. SMM) and heavy vs. light-chain status. The treatment period will be 6 months and primary outcome assessments as outlined below will occur at baseline and after 6 months of treatment or for those that discontinue medication, as close to the 6-month timepoint as possible. To explore participants' willingness to continue to take metformin after the 6-month treatment period and observe longer-term response, participants will be given the option to learn their treatment assignment after completing the primary study endpoints. Any participant randomized to the metformin group will be invited to continue to take metformin for an additional 6 months.

Treatment will be administered on an outpatient basis. Reported adverse events and potential risks are described in Section 7. Appropriate dose modifications are described in Section 6.

Participants will dose escalate in a stepwise fashion beginning with 500mg and increasing by 500mg until they reach 1500mg. The duration of this study and corresponding treatment period is 6 months.

No investigational or commercial agents or therapies other than those described below may be administered with the intent to treat the participant's premalignancy.

5.1 Unblinding

In the event of a medical emergency where breaking the blind is required to provide medical care to the subject, the primary investigator or treating investigator with approval by the primary-investigator may obtain the treatment assignment directly from the research pharmacy. Blinding of study treatment is critical to the integrity of this clinical trial and therefore, if a subject's treatment assignment is disclosed to the investigator, the subject will have study treatment discontinued. Documentation of the decision to unblind will be recorded in the subject's medical record.

After primary outcome measures are collected (blood collection at 6 month end of treatment visit), participants will have the option to learn their treatment assignment (be unblinded) and any patients randomized to the metformin arm will be invited to continue to take metformin for an additional 6 months on a crossover arm. Participants randomized to the placebo will discontinue study medication at the 6-month time point.

In addition, at the end of the study the PI will obtain a list from the research pharmacy of each patient's randomization for data analysis.

5.2 Treatment Regimen

Metformin and its corresponding placebo are the proposed pharmacological treatments. Metformin can be safely used in nondiabetics without significantly impacting quality of life. Minor adverse events associated with this agent are nausea/vomiting, diarrhea, or constipation. All patients will be cautioned against excessive alcohol intake, either acute or chronic, when taking metformin, since alcohol intake potentiates the effect of metformin on lactate metabolism.

A cycle is defined as 28 days. In the absence of toxicity, withdrawal or other event, treatment may continue for up to 6 cycles. The metformin dose will be 1500 mg/day, provided in 500 mg pills. To minimize gastrointestinal symptoms, metformin will be started at a low dose of 500 mg (1 pill) and the patient will be advised to take it with food at water. A drug dairy/schedule will be provided for each patient for the duration of the treatment period, and telephone contact will be made periodically to assess compliance and toxicity.

As noted in the study calendar, adherence to the medication will be assessed throughout the study period by means of telephone calls at day 7, day 28, day 48 (optional at the discretion of clinical team), at the end of cycle 3, and at the end of study visit within the window specified (Section 10 Study Calendar footnote 10). All remaining pills will also be returned to study staff and counting will occur in the DFCI research pharmacy.

Please refer to section 6.1 for criteria and guidance for dose escalation.

As this is a blinded study, all participants will be asked to adhere to this dosing schedule and the pill-taking guidelines specified below. Therefore, the dosing regimen for the placebo is the same as described above for metformin.

Week 1 (Days 1-7)

Agent	Dose	Route	Schedule
-------	------	-------	----------

Metformin/Placebo	500mg	Oral	Once daily with meals and at least 8 ounces of water
-------------------	-------	------	--

Week 2-4 (Days 8-28)

Agent	Dose	Route	Schedule
Metformin/Placebo	1000mg	Oral	Once daily with meals and at least 8 ounces of water

Week 5 through week 24 (Day 29 through end of study)

Agent	Dose	Route	Schedule
Metformin/Placebo	1500mg	Oral	Once daily with meals and at least 8 ounces of water

NOTE: The participant will be required to maintain a medication diary of each dose of medication. The medication diary will be returned to clinic staff at their 6-month/end of study visit or mailed back along with any extra medication to the study team to perform accountability per local policies.

Patients will be invited to continue to take metformin for an additional 6 months on a crossover arm after completing the study's primary endpoints. This option will only be available to individuals who are taking metformin during the blinded study phase. Patients taking placebo will discontinue all study medication at the 6-month timepoint.

Optional Extended Treatment Period (crossover arm): Week 24-48.

Agent	Dose	Route	Schedule
Metformin	1500mg or highest tolerated dose	Oral	Once daily with meals and at least 8 ounces of water

NOTE: A new open-label metformin diary will be provided to participants who wish to participate in the optional extended treatment period. As done previously, the medication diary will be returned to clinic staff at the end of the additional 6-month treatment period or mailed back along with extra medication to the study team to perform accountability per local policies.

5.3 General Concomitant Medication and Supportive Care Guidelines

Participants may receive any supportive care necessary to address side effects of metformin so long as it is not considered investigational.

5.4 Prohibited Medications and Procedures

There are several medications and procedures which may increase the risk of lactic acidosis associated with metformin. Medical records will be reviewed for potential metformin contraindications including but not limited to the following: acetazolamide (Diamox), dichlorphenamide (Keveyis), methazolamide, topiramate (Topamax, in Qsymia), or zonisamide (Zonegran). In addition, participants will be advised to tell the study team if they plan to have surgery or any medical procedures requiring iodinated contrast agents, which can also increase the risk of lactic acidosis. In the event of a surgery or procedure that requires a contrast agent, participants will be advised to stop taking study medication 48 hours prior to the procedure and to refrain from re-starting study medication until they have undergone a blood test showing normal kidney function.

Participants are also prohibited from taking any investigational medications, or any cancer directed therapy during the study. In the event that a cancer-directed therapy is clinically warranted (e.g., progression to MM), participants will come off study so that appropriate care can be received.

5.5 Agent Administration

Participants will be provided 3 months of study medication at study entry after randomization; the remaining pills will be mailed to the patient at a later date to minimize drug waste per local policies. A drug diary will also be provided for participants to record study drug compliance/adherence. Participants in the extended treatment (crossover arm) will receive a 3-month supply of medication in person or by mail at the 6-month visit if eligible. To minimize drug waste and ensure patient safety, the final 3-month supply will be sent to participants at a later date once safety labs are reviewed by the research team.

The Office of Data Quality (ODQ) will have a randomization schedule which has been prepared and provided by the Study Statistician. Study agent randomization to placebo or active SDG will be provided for each sequential post-randomization study ID number and sent by ODQ to the research pharmacy.

Both Metformin and matched placebo are to be provided by the DFCI Research Pharmacy. Metformin (containing 500 mg of the active ingredient) placebo (containing the same filler material but without the active ingredient) will be given to all trial participants for the 6 months of participation (two shipments each containing a 3-month supply). All subjects should have off-study procedures ideally no later than 7 days of the last dose of Metformin or placebo. However, if a participant stops study agent prematurely in an unscheduled situation, s/he should come in for re-assessment as early as possible. Participants in the crossover arm will be provided 1500 mg Metformin by the DFCI Research Pharmacy. As indicated previously, the pills will be given in two batches, each containing a 3-month supply. All participants in the crossover arm should also have off-study procedures ideally no later than 7 days of the last dose of Metformin.

Metformin/Placebo tablets (Study Drug) are to be taken orally and tablets are to be taken whole, not broken or crushed. Study drug will be administered or dispensed only to eligible patients under the supervision of the investigator or identified sub investigator(s). As described above, it is recommended that all tablets are taken with food to minimize gastrointestinal side effects.

Please refer to section 8 for further information about the study agent.

5.6 Participant Diary

Participants should be instructed to document all oral study drug administration on a patient diary and return unused tablet and packaging for review of compliance at the end of the study. Sites are responsible to maintain the diary as source documentation.

5.7 Removing a Participant from Treatment (Off Treatment)

Duration of therapy will depend on individual response, evidence of disease progression and tolerance. In the absence of toxicity or withdrawal from therapy, treatment may continue for up to 6 cycles when each cycle is defined as 28 days (or 12 cycles for those in the crossover arm), or until one of the following criteria applies:

- Disease progression to overt MM
- Intercurrent illness that prevents further administration of treatment
- Unacceptable adverse event(s) or co-morbid condition
- Participant demonstrates an inability or unwillingness to comply with the oral medication regimen and/or documentation requirements
- Participant decides to withdraw from the protocol therapy
- General or specific changes in the participant's condition render the participant unacceptable for further treatment in the judgment of the treating investigator

Participants will be removed from the protocol therapy when any of these criteria apply. The reason for removal from protocol therapy, and the date the participant was removed, must be documented in the case report form (CRF). Alternative care options will be discussed with the participant.

When a participant is removed from protocol therapy and/or is off of the study, the participant's status must be updated in OnCore in accordance with [REGIST-OP-1](#).

5.8 Duration of Follow Up

The total study intervention period is 6 months, with the final assessment occurring at the end of the scheduled 6-month treatment period. However, some participants may choose to be unblinded after primary outcome assessments are complete and will agree to continue to take metformin for an additional 6-month observational period (crossover arm). In addition, participants will be followed for survival and disease events via medical record review for up to 5-years after randomization.

5.9 Removing a Participant from Study (Off Study/Off Follow Up)

Participants will be removed from study when any of the following criteria apply:

- Lost to follow-up
- Withdrawal of consent for data submission
- Death
- Progression to overt MM

The reason for taking a participant off study, and the date the participant was removed, must be documented in the case report form (CRF). In addition, the study team will ensure the participant's status is updated in OnCore in accordance with [REGIST-OP-1](#).

6. DOSING DELAYS/DOSE MODIFICATIONS

The major toxic effects of which limit metformin dose are gastrointestinal (nausea, abdominal bloating, diarrhea). Dose adjustments, for reasons of toxicity will be as in the tables below. Please note that none of the recommended dose adjustments require splitting of the study drug.

If multiple adverse events are seen, dose modifications should be based on the worst preceding toxicity. The AE should be attributed to a specific drug, if possible, so that the dose modifications can be made accordingly. Reduction of the study drug is appropriate if toxicity is thought to be primarily related to the agent under study.

The dose modification guidelines should be regarded as guidelines and should be followed unless otherwise discussed with the principal investigator.

Reductions are based on toxicity noted within a cycle and may contribute to the dose level for the subsequent cycle. Dose re-escalation can be considered after discussion with the treating investigator. Each cycle is defined as 28 days.

Dose delays and modifications will be made as indicated in the following table(s). The descriptions and grading scales found in the revised NCI Common Terminology Criteria for Adverse Events (CTCAE) version 5.0 will be utilized for dose delays and dose modifications. A copy of the CTCAE version 5.0 can be downloaded from the CTEP website http://ctep.cancer.gov/protocolDevelopment/electronic_applications/ctc.htm.

6.1 Criteria to Escalate- Gastrointestinal Toxicity

6.1.1 Criteria to Escalate from 500mg to 1000mg

1. Participants must not have any gastrointestinal toxicity > Grade 1 on day of anticipated escalation
 - If toxicity is Grade 2, hold for one week, and re-evaluate
 - If in one week, the toxicity has not resolved to Grade 1 or better, hold treatment for a second week and re-evaluate
 - If the participant is unable to dose escalate after 3 weeks beyond the expected escalation date, consider treatment at 500mg for the duration of the study or discontinuation at PI discretion
 - If toxicity is Grade 3, hold medication for 1 week, and re-evaluate
 - If in one week, toxicity has not resolved to Grade 1 or better, consider holding for one additional week, and re-evaluate
 - If the participant is unable to dose escalate after 3 weeks beyond the original expected escalation date, or without resolution of symptoms to Grade 1, maintain 500mg as final dose for the duration of the study, or discontinue altogether at the investigator's discretion

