6.1.2 Criteria to Escalate from 1000mg to 1500mg

1. Participants must not have any gastrointestinal toxicity > Grade 1 on day of anticipated escalation
 - If toxicity is Grade 2, hold for one week, and re-evaluate
 - If in one week, the toxicity has not resolved to Grade 1 or better, hold treatment for a second week and re-evaluate
 - If after the second week the toxicity has not resolved to Grade 1 or better, consider holding for one additional week
 - If the participant is unable to dose escalate after 3 weeks beyond the expected escalation date maintain at 1000mg or reduce to 500mg for the duration of the study or discontinue treatment at PI discretion
 - If toxicity is Grade 3, hold for 1 week, and re-evaluate
 - If in one week toxicity has not resolved to Grade 1 or better, consider holding for one additional week, and re-evaluate
 - If the participant is unable to dose escalate after 3 weeks beyond the expected escalation date, or without resolution of symptoms to Grade 1 or better, discontinue treatment at PI discretion.

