6.3 Dose Modification Schedule

Dose Level	Dose
0 (Starting Dose)	1500mg Daily
-1	1000mg Daily
-2	500mg Daily
-3	Discontinue

Dose Level	Dose
------------	------

0 (Starting Dose)	1000mg Daily
-1	500mg Daily
-2	Discontinue

Dose Level	Dose
0 (Starting Dose)	500mg Daily
-1	Discontinue

- With the investigator's discretion, dose re-escalation can be considered, or an alternative dose ramp up plan or dose management plan proposed
- If a participant needs to be dose reduced during the dose ramp up period, the principal investigator may decide to not escalate further, or escalate after improvement of symptoms

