6.4 Toxicity Management Guidelines For Toxicity After Escalation Period

The following guidelines should be followed if thought to be related to the study medication:

Nausea, Vomiting, Diarrhea	Management/Next Dose for Study Drug
≤ Grade 1	No change in dose. Patient should be encouraged to remain on full dose; if unwilling to remain on therapy, stop study treatment for one week. Resume at same dose. If symptoms recur, then reduce to one tablet daily (if applicable) permanently for remainder of study.
Grade 2	Hold until ≤ Grade 1. Resume at one dose level lower, if indicated at PI discretion.
Grade 3	Hold* until ≤ Grade 1. Resume at 1-2 dose levels lower, if indicated at PI discretion.
Grade 4	Off protocol therapy
Recommended management: antiemetics or Loperamide antidiarrheal therapy as needed	

Other Toxicity*	Management/Next Dose for Study Drug
≤ Grade 1	No change in dose. Patient should be encouraged to remain on full dose; if unwilling to remain on therapy, stop study treatment for one week. Resume at same dose. If symptoms recur, then reduce to one dose level

	lower permanently for remainder of study.
Grade 2	Hold until \leq Grade 1. Resume at one dose level lower, if indicated at PI discretion.
Grade 3	Hold until \leq Grade 1. Resume at 1-2 dose levels lower, if indicated at PI discretion.
Grade 4	Off protocol therapy

* all other toxicities include any other hematologic or non-hematologic toxicity that is not listed specifically above.

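### The Grade 3 rule at the 500 mg step permits 500 mg to continue while toxicity is unresolved, which does not fit the 1000 mg step or the hold condition in 6.4

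*Combined protocol and SAP*

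**What the plan says.** Section 6 of the protocol sets escalation rules for gastrointestinal toxicity (6.1) and for all other toxicity thought related to study drug (6.2). Each has a 500 to 1000 mg step and a 1000 to 1500 mg step, and the 6.2 wording repeats the 6.1 wording for Grade 3.

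- **500 mg step (6.1.1, 6.2.1).** The first action for Grade 3 is explicit that drug stops: "If toxicity is Grade 3, hold medication for 1 week, and re-evaluate". A second week of holding may be considered. The last bullet covers a participant who cannot escalate three weeks after the step was due "or without resolution of symptoms to Grade 1, maintain 500mg as final dose for the duration of the study, or discontinue altogether". The choice is left to the investigator.
- **1000 mg step (6.1.2, 6.2.2), Grade 3.** The matching bullet covers a participant who cannot escalate after three weeks "or without resolution of symptoms to Grade 1 or better, discontinue treatment at PI discretion". No other outcome is listed.
- **1000 mg step, Grade 2.** For a participant who cannot escalate after three weeks, the options are "maintain at 1000mg or reduce to 500mg for the duration of the study or discontinue treatment at PI discretion".
- **6.3.** The dose ladder has nothing below 500 mg except discontinuation. A note on ramp-up says that, if a reduction is needed, "the principal investigator may decide to not escalate further, or escalate after improvement of symptoms". Another note lets the investigator propose a different ramp-up or dose plan.
- **6.4**, headed "Toxicity Management Guidelines For Toxicity After Escalation Period". Related Grade 2 toxicity is held until Grade 1 or lower, then resumed one level lower if indicated. Grade 3 is held on the same condition, then: "Resume at 1-2 dose levels lower, if indicated at PI discretion".

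**The concern.** The bullet in 6.1.1 and 6.2.1 joins two different clinical states with a single 'or': toxicity that has come down but left the participant unable to escalate in time, and toxicity that has not come down to Grade 1. Both receive the same two options. For the second state, one option is to go back on the dose that was being held because of that toxicity.

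The other rules for a comparable participant do not list that option. What is at stake is a participant-safety instruction on which a site needs a single clear reading. The trial-level safety rules in 12.9 respond to related Grade 4 and 5 events, so persistent Grade 3 toxicity is handled mainly by section 6.

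**Working it through.** No arithmetic applies, because the protocol gives no figure on this point. The check is to follow one state through each rule: Grade 3 toxicity, drug held, not resolved to Grade 1 (so still Grade 2 or higher).

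| Where | Outcomes listed for the unresolved state | Who decides |
|---|---|---|
| 6.1.1, 6.2.1 (500 mg step) | Keep 500 mg as final dose, or discontinue | Investigator |
| 6.1.2, 6.2.2 (1000 mg step) | Discontinue | PI |
| 6.4 (after escalation, related toxicity) | Keep holding until Grade 1 or lower; only then resume at a lower level, if indicated | PI |
| 6.3 (ladder, from 500 mg) | Next level down is discontinuation; the section has no hold rule | Notes leave room for discretion |

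1. **Does 6.1.1 permit dosing while unresolved?** Yes, on its wording. The unresolved limb stands as an alternative to the three-week limb, and the options that follow attach to both. Because the Grade 3 instruction has already stopped the drug, keeping 500 mg as the final dose means restarting it.

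2. **Does the 1000 mg step treat the same state alike?** No. 6.1.2 also joins the two limbs with 'or', but lists only discontinuation. A general policy against staying or reducing at that step does not explain this, since the Grade 2 bullet there lists both. So a continuing option is listed at the dose with nothing beneath it, and none is listed at the dose that has 500 mg beneath it.

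3. **Does 6.4 bear on it?** Not on the day of the planned escalation, because its heading limits it to the period afterwards. Once 500 mg has been fixed as the final dose, however, no further escalation is due and 6.4 becomes the operative table for related toxicity. A participant placed there with Grade 2 or 3 toxicity meets its hold instruction at once. The two instructions cannot both be followed.

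4. **Does 6.3 contradict 6.1.1?** Not by itself. It lists dose levels without grade triggers. It matters only because 6.4 speaks of resuming at a lower level, and from 500 mg the ladder offers no lower dose.

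5. **Do 6.2.1 and 6.2.2 differ?** No. The same pair of bullets appears there, so the inconsistency covers gastrointestinal toxicity and all other toxicity thought related.

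**The case against.** The strongest reply is that this is discretion working as intended. Discontinuation is open at both steps. Section 6 describes its rules as guidelines that may be departed from after discussion with the PI, and 6.3 expressly allows alternative dose plans during ramp-up. Section 5.7 removes participants for unacceptable adverse events. Different rules at different doses can be deliberate. The bullet could also be read as pairing the two states with the two outcomes in turn: 500 mg for those who merely could not escalate, discontinuation for those unresolved.

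Much of this stands, and it limits the point in several ways.

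- A reader might infer that the protocol requires re-exposure, or handles the same event in opposite ways at the two steps. It does not: continuing is one of two options at 500 mg, and the 1000 mg rule is itself discretionary.
- A reader might infer that 6.3 and 6.4 forbid 500 mg on the escalation day. They do not: 6.3 has no hold rule, and 6.4 starts later.
- A reader might work out a length of exposure from the three-week limit. The unresolved limb carries no three-week condition, so that figure would rest on the wrong trigger.
- A reader might expect the effect to fall mainly on the metformin arm, or to vary with which table a site consults. The blinded rules apply to both arms, and the documents give no toxicity rates by arm and nothing about differences between sites.

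What the reply does not remove is the text itself. The paired reading is possible, but the bullet does not state it. Discretion does not reconcile default instructions that list different options for the same state. That 6.4 would halt dosing once 500 mg is final confirms the conflict with the bullet that placed the participant there.

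**Conclusion.** The point holds as an internal inconsistency in a safety instruction. The last Grade 3 bullet in 6.1.1 and 6.2.1, read literally, permits dosing at 500 mg through Grade 3 toxicity that has not resolved to Grade 1. The corresponding bullets in 6.1.2 and 6.2.2 list no such option, and the 6.4 hold condition conflicts with it once escalation is over.

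The firmest part is the comparison between the two escalation steps, which needs no inference. The conflict with 6.4 rests on two assumptions: that fixing 500 mg as the final dose ends the escalation period, and that the toxicity is thought related to study drug.

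The extent is two bullets set against two bullets and one table condition. How many participants would be affected cannot be stated, because the documents give no expected rate of Grade 3 toxicity at 500 mg. Nothing in them shows an effect on the intention-to-treat primary analysis. The wording should be corrected because it concerns participant safety and is cheap to correct; it does not threaten the trial's main result.

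**What to change.** Reconcile the last Grade 3 bullets of 6.1.1 and 6.2.1 with those of 6.1.2 and 6.2.2 and with the hold condition in 6.4. In doing so, split the joined condition and state separately what applies (a) when toxicity has resolved to Grade 1 or better but escalation was not possible in time, and (b) when it has not resolved. State also when 6.4 takes over from the escalation rules.

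The sponsor's clinicians decide the outcome in each case. The outcomes need not be the same at both dose steps, provided that any difference is stated and intended.

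The cost is a wording change in an amendment, with no extra participants, visits or procedures.

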Despite the promise of early treatment in the precursor MM disease setting, it has remained highly controversial given the high cost and risk of toxicity and harm to patients who may never progress to overt MM.¹⁴⁻¹⁶ For example, the treatments currently being investigated in the precursor disease setting carry considerable short- and long-term risks, including but not limited to arterial thromboembolic events, neutropenia and thrombocytopenia, and increased risk for secondary malignancies.¹⁷ These toxicities, in effect, mostly limit the use of existing therapies to the highest risk patient subsets. Therefore, the identification lower-risk, cost-effective strategies to prevent disease progression in patients with less aggressive forms of MGUS and SMM is of considerable importance.

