9.2 Final assessments

End of Study primary outcome assessments should ideally be done within 7 days of completing 6 months of treatment, or for those that were not able to complete 6 months of treatment, as close to the 6 month timepoint as possible. At this visit, a study staff member will collect pill bottles in person or by mail (empty and unused), participants will have 6-month research blood draw and clinical labs performed, bone marrow samples collected if being done as part of standard of care procedures, have weight measured and recorded, and be asked to complete the Final Questionnaire. For individuals who agree to continue to take metformin for an additional 6-months after primary outcomes are assessed, these secondary outcomes will ideally be done within 7 days of completing 12-months of treatment, or as close to that timepoint as possible. Similar to the 6-month assessment, a study staff member will collect pill bottles in person or by mail, participants will have a research blood draw and clinical labs performed, and bone marrow core biopsy/aspirate samples collected if being done as part of standard of care procedures. At this time, weight will be measured and recorded.

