12.2 Statistical Analysis

The primary hypothesis being tested in this trial is that patients randomized to metformin will experience a significant reduction in M-protein levels compared to patients randomized to the placebo. This parameter has been selected as the primary endpoint because of its known clinical utility in predicting progression to overt MM in MGUS and SMM patients.⁶⁷⁻⁶⁹ Changes in this endpoint will be evaluated from baseline to follow-up in the two groups using a repeated measures mixed-effects model that accounts for the correlation between baseline and follow-up measures and is generally robust to missing data. The baseline value of the dependent variable (M-protein level) and disease subtype will be included as covariates in the regression models. Group-by-time interaction terms will be included as fixed-effects in the regression model. Model fit will be assessed using standard methods. Primary analysis of this endpoint will utilize stratified testing and intention-to-treat methods, using data from all participants randomized to an intervention group.⁷² Secondary/exploratory analyses will evaluate the influence of metformin on M-protein level in a per-protocol analysis.

A study project manager who is not involved in the statistical analysis will request information on treatment allocation from the DFCI Research Pharmacy. The Research Pharmacy is permitted to give the project manager information after the trial is closed to accrual and data collection on primary endpoints have been completed. However, all individuals performing the statistical analysis will remain blind to treatment group (metformin vs. placebo) for the primary outcome analysis.

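### The last Grade 3 step at 500 mg (6.1.1 and 6.2.1) can be read to allow continued dosing while toxicity is still above Grade 1, which is looser than the protocol's other Grade 3 rules

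*Combined protocol and SAP*

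**What the plan says.** Section 6.1 governs escalation when there is gastrointestinal toxicity. Section 6.2 does the same for other toxicities judged at least possibly related to study drug. Each covers two dose steps (500 to 1000 mg and 1000 to 1500 mg), and each step has a Grade 2 and a Grade 3 branch.

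- **500 to 1000 mg, Grade 3 (6.1.1, repeated in 6.2.1).** Drug is held for a week, and a second week may be considered. The final step applies to a participant who cannot escalate within three weeks of the planned date, or who is "without resolution of symptoms to Grade 1, maintain 500mg as final dose for the duration of the study, or discontinue altogether". The choice is left to the investigator.
- **1000 to 1500 mg, Grade 3 (6.1.2, repeated in 6.2.2).** The holds are the same. The final step for a participant who cannot escalate, or who is "without resolution of symptoms to Grade 1 or better, discontinue treatment at PI discretion", names no dose to stay on.
- **After escalation, Grade 3 (6.4).** Drug is held until toxicity is Grade 1 or lower. Only then does the table say "Resume at 1-2 dose levels lower, if indicated at PI discretion".
- **Dose levels (6.3).** The level below 500 mg is discontinuation.
- **Status of these rules (opening of Section 6).** They "should be regarded as guidelines and should be followed unless otherwise discussed with the principal investigator".

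**The concern.** The final step in 6.1.1 and 6.2.1 names failure to recover to Grade 1 as a trigger, then lists staying on 500 mg for the rest of the study as one of two responses. It does not make that response conditional on recovery. A site following the text could restart or continue 500 mg for months in a participant whose toxicity began at Grade 3 and has not cleared, and would still be within the protocol. Elsewhere in Section 6 the Grade 3 rules either stop drug or hold it until recovery. What is at stake is the safety of the few people who reach this step, and consistent handling of them. Sample size, type I error, power and the estimate of the M-protein effect are not at issue.

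**Working it through.** No formula applies, so the check is a comparison of text. The table shows the action each rule names when Grade 3 toxicity has not come back to Grade 1.

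| Section | Setting | Action named | Whose discretion |
|---|---|---|---|
| 6.1.1 | Gastrointestinal, 500 to 1000 mg | Stay on 500 mg, or discontinue | Investigator |
| 6.2.1 | Other related toxicity, 500 to 1000 mg | Stay on 500 mg, or discontinue | Investigator |
| 6.1.2 | Gastrointestinal, 1000 to 1500 mg | Discontinue | PI |
| 6.2.2 | Other related toxicity, 1000 to 1500 mg | Discontinue | PI |
| 6.4 | Any related toxicity, after escalation | Keep holding; no restart until Grade 1 or lower | PI (on resumption) |

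**Count.** There are 2 toxicity types × 2 dose steps = 4 Grade 3 final steps. Continued dosing is listed in 2 of 2 at 500 mg and 0 of 2 at 1000 mg.

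**Who meets the trigger.** The trigger is non-resolution to Grade 1. It covers toxicity still at Grade 3 and toxicity that has improved only to Grade 2.

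**Does the contrast extend beyond Grade 3?** No. For a participant who started at Grade 2 and cannot escalate, 6.1.1 and 6.2.1 allow 500 mg, and 6.1.2 and 6.2.2 allow 1000 mg or a reduction to 500 mg. The inconsistency is confined to the Grade 3 branch.

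**Consistency with 6.3 and 6.4.** Suppose a participant on 500 mg has Grade 3 toxicity after escalation and it resolves. Section 6.4 points to a lower dose level, and by 6.3 none exists below 500 mg. Under 6.1.1 or 6.2.1, a participant whose Grade 3 toxicity has not resolved may stay on 500 mg. Taken literally, the less recovered participant has the looser rule.

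**Number affected.** With 60 participants randomized 1:1, 60 × 1/2 = 30 receive metformin in the blinded period. The documents give no Grade 3 rate at 500 mg, so no expected count can be derived.

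**The case against.** The strongest reply has four parts.

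1. **Section 5.7 already protects the participant.** A reader might take 5.7 as merely permitting removal. In fact it says participants will be removed when a listed criterion applies, and one criterion is "Unacceptable adverse event(s) or co-morbid condition". That is a real limit on the risk. But it sets no grade threshold and turns on a judgement of what is unacceptable, so it does not correct a specific option pointing the other way.

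2. **Section 6.4 may apply.** Once 500 mg is declared final, escalation for that person is arguably over, and 6.4 would require a hold. That reading is fair. If it is right, 6.4 contradicts the written option in 6.1.1 and 6.2.1, and the text still needs mending.

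3. **The sentence is ambiguous.** It joins two triggers to two outcomes. One can pair them in order: unable to escalate leads to 500 mg, and unresolved toxicity leads to discontinuation. This cannot be excluded, which is why the point is that the step can be read to allow continued dosing. The pairing is not clean, however. The only stated bar to escalation in these sections is toxicity above Grade 1, so someone unable to escalate will ordinarily be someone whose toxicity has not resolved.

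4. **Everything here is discretionary.** Staying on 500 mg is an option beside discontinuation. Discontinuation in 6.1.2 and 6.2.2 is itself at PI discretion, Section 6 calls its rules guidelines, and 6.3 allows an alternative dose management plan. More latitude at the lowest dose could also be defended. All this stands and keeps the point minor. It does not explain why the two dose steps name different options for the same state.

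Two stronger readings should be set aside. A reader might infer that the protocol contradicts its own rationale, since Section 2.2 warns of "risk of toxicity and harm to patients who may never progress to overt MM". That sentence concerns the myeloma therapies being tried in precursor disease, and it serves to argue for lower-risk options; it says nothing about metformin 500 mg. A reader might also infer that Section 6 otherwise never allows dosing with toxicity above Grade 1. The Grade 2 branches show that it does.

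**Conclusion.** The point holds as a minor patient-safety inconsistency, limited to the Grade 3 branch. Two of the four Grade 3 final steps can be read to allow 500 mg to continue to the end of the study without recovery to Grade 1; the other two, and 6.4, do not. The conclusion rests on reading both outcomes in 6.1.1 and 6.2.1 as open to a participant who has not recovered, which is the natural reading but not the only one. The documents do not support saying that continued dosing is required, that 5.7 leaves such a participant unprotected, or that any particular number of people would be affected. There is no effect on the primary analysis.

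**What to change.** In the final Grade 3 bullet of 6.1.1 and of 6.2.1, allow 500 mg to be kept as the final dose only after drug-related toxicity has resolved to Grade 1 or better; otherwise discontinue. Limiting the condition to drug-related toxicity matters in 6.1.1, because Section 6.1, unlike 6.2, is not confined to related events, and nobody should have to stop for symptoms with another cause. A participant who recovers but should not escalate can still stay on 500 mg. No further change to the Grade 4 rules is needed for this point.

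The cost is one condition in two bullets, with no added visits, tests or participants. The downside is that a few participants may stop drug early. They are still assessed: Section 9.2 schedules the final visit "for those that were not able to complete 6 months of treatment, as close to the 6 month timepoint as possible". They also stay in the primary intention-to-treat analysis, which Section 12.2 defines as "using data from all participants randomized to an intervention group".
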